9.5. Week 2, Week 4, and Week 6 After Discharge

- PO drug administration:
 - o PO clindamycin 13 mg/kg/dose q8h in subjects with proven MRSA infection due to clindamycin susceptible MRSA or when no pathogen is isolated.
OR
 - o PO cephalexin 25 to 33 mg/kg/dose q 8 hours in subjects with proven MSSA infection.
OR
 - o PO linezolid 600 mg q12h (Children > 12 years old) or 10 mg/kg q8h (children <=12 years old) in subjects with clindamycin-resistant MRSA pathogens.

Clinical Assessments - any time during study day (assessments will be performed for research unless they are already being performed per standard of care; exceptions are indicated):

- o Obtain an interval medical and surgical history focusing on the involved extremity, including history

of surgical procedures for complications of hematogenous SA osteomyelitis (eg, drainage of the bone) and all active conditions from the following categories.

- o Record concomitant medications (Section 8.3). For subjects who are being breast fed, record all medications taken by the lactating mother.
- o Record vital signs: resting pulse, blood pressure, and respiratory rate.
- o Record adjunctive therapeutic procedures (eg, surgeries).
- o Record standard of care radiology results.
- o Evaluate and record physical findings of hematogenous SA osteomyelitis (eg, warmth, tenderness, swelling, erythema, and movement of the infected extremity). Most of the subjects are expected to have surgical incision and drainage procedures and thus assessing the extremity for swelling, erythema, warmth and tenderness may not be possible because of drains in place and large surgical dressings that cannot be removed. The degree of the subject's ability to ambulate will be assessed if the osteomyelitis is in the lower extremity- ie. walks unaided, able to bear weight, can walk aid using a walker, etc. The use of upper and lower extremities will be assessed in terms of movement and range of motion.
- o Assess clinical outcome (site of infection has complete resolution of pain, swelling and warmth and the patient is able to use the affected extremity normally and is back to normal activities).
- o Identify, assess, and record any new or ongoing AEs or SAEs.

Laboratory Assessments - any time during study day, but before starting PO study drug, if applicable (assessments will be performed for research unless they are already being performed per standard of care; exceptions are indicated):

- o Collect CRP and ESR lab results, if clinically indicated for standard of care.
- o If clinically indicated, estimate CrCl using the updated Schwartz "bedside" formula (Schwartz et al, 2009).

9.6. End of Antibiotic Therapy (EOT)/Week 4/ OR Week 6

Note that EOT visit and assessments may occur at the Week 4 visit or the Week 6 visit. If the EOT visit occurs on the same day as the Week 4 or Week 6 visit, only the EOT visit will be recorded in CTMS.

- If applicable, as PO drug may or may not be given on the same calendar day as EOT assessments, administer PO drug as described in Section 9.2.
- Clinical Assessments - any time during visit (assessments will be performed for research unless they are already being performed per standard of care; exceptions are indicated):

- o Record concomitant medications (Section 8.3). For subjects who are being breast fed, record all medications taken by the lactating mother.
- o Record height and weight.
- o Record vital signs: resting pulse, blood pressure, respiratory rate and temperature.
- o Record adjunctive therapeutic procedures (eg, surgeries), if performed.
- o Record standard of care radiology results.
- o Evaluate and record physical findings of hematogenous SA osteomyelitis (eg, warmth, tenderness, swelling, erythema, and movement of the infected extremity). The degree of the subject's ability to ambulate will be assessed if the osteomyelitis is in the lower extremity- ie. walks unaided, able to bear weight, can walk aid using a walker, etc. The use of upper and lower extremities will be assessed in terms of movement and range of motion.
- o Assess clinical outcome (site of infection has complete resolution of pain, swelling and warmth and the patient is able to use the affected extremity normally and is back to normal activities).
- o Identify, assess, and record any new or ongoing AEs or SAEs

- Laboratory Assessments (Local Laboratory) - any time during visit, Collect CRP and ESR lab results, if clinically indicated for standard of care.
 - o Obtain urine sample for urine pregnancy (for a female who has reached menarche).
 - o If clinically indicated, estimate CrCl using the updated Schwartz "bedside" formula (Schwartz et al, 2009).

9.7. Follow Up

Conduct FU assessments 12 months after administration of the last dose of the drug (IV or PO whichever is the latest).

- Clinical Assessments - any time during visit (assessments will be performed for research unless they are already being performed per standard of care; exceptions are indicated):
 - o Record concomitant medications (Section 8.3). For subjects who are being breast fed, record all medications taken by the lactating mother.
 - o Record vital signs: resting pulse, blood pressure, respiratory rate and temperature.
 - o Record adjunctive therapeutic procedures (eg, surgeries).
 - o Record standard of care radiology results.
 - o Assess clinical outcome (site of infection has complete resolution of pain, swelling and warmth and the patient is able to use the affected extremity normally and is back to normal activities).
 - o Identify, assess, and record event such as pathologic fractures and growth disturbances.
 - o Laboratory Assessments - any time during visit:

- o If clinically indicated, estimate CrCl using the updated Schwartz "bedside" formula (Schwartz et al, 2009).

9.8. Safety Lab Tests

9.8.1. Study Required Lab Tests

Alkaline Phosphatase, Bilirubin, AST, ALT and Direct Coombs (DATscreen) will be obtained within 24 hours prior to enrollment; and at the completion of ceftaroline treatment (EOIV visit).

Isolate susceptibilities: The ceftaroline MIC of *S. aureus* isolates or other isolates such as Group A streptococcus, *Streptococcus pneumoniae* or *Kingella kingae* that are obtained from the patients with acute hematogenous osteomyelitis will be determined using Clinical and Laboratory Standards Institute (CLSI) methods. These will be performed in the CAP certified Infectious Disease Research Laboratory. CLSI interpretive breakpoints will be used to determine if the isolate is susceptible, intermediate or resistant to ceftaroline. The samples will be obtained from pathology (from already collected samples) to conduct the Isolate susceptibility studies.

9.8.2. Standard of Care Labs

Record the following local safety labs if performed per standard of care: hemoglobin, hematocrit, WBC, platelet count, BUN, serum creatinine, CRP and ESR. If multiple laboratory tests are obtained on the same day, record test results closest to administration of study drug.

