6.1. Outcome Measures

Primary: Safety evaluations will be conducted in the children who have started treatment with ceftaroline. Assessments will include:

- AEs, SAEs, deaths, and discontinuations due to SAEs.
- Vital signs and laboratory parameters.

Secondary:

- Clinical response (the subject has been afebrile for at least 48 hours, has negative blood cultures, is clearly improving in general, is able to eat and drink, and is able to use or move the involved extremity) at the end of parenteral therapy (approximately days 5 to 14) by subject and by baseline pathogens although *S. aureus* is expected to be the predominant pathogen.
- Clinical outcome (site of infection has complete resolution of pain, swelling and warmth and the patient is able to use the affected extremity normally and is back to normal activities) at the EOT and at the one year follow up visit.

- Clinical relapse within a year of enrollment in the study or the development of a pathologic fracture.

PK:

- Concentrations of ceftaroline fosamil, ceftaroline, and ceftaroline M-1 in plasma.
- If available, concentrations of ceftaroline fosamil, ceftaroline, and ceftaroline M-1 in purulent material such as bone or subperiosteal abscess or synovial fluid.

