7.7. Subject Discontinuation or Withdrawal

Subjects should be encouraged to complete all study outcome assessments. However, a subject may be discontinued from study drug or may withdraw assent/consent to participate in this study at any time without penalty or loss of benefits to which the subject is otherwise entitled. Subjects will be assessed for safety of ceftaroline at the time points outlined in the schedule of evaluations, if possible.

7.7.1. Off Study Criteria:

- Subjects who require continued home parenteral antibiotics will be discontinued from the study.
- Subjects that require IV treatment after switching to Oral drug.
- If a subject's estimated CrCl decreases to < 50 mL/min during the treatment period, the subject will be discontinued from the study.
- Diarrhea (the occurrence of > 4 loose stools /day) with blood or mucus
- Moderate to severe maculopapular rash that does not resolve following administration of diphenhydramine (Benadryl®) or any urticarial rash.
- Absolute neutrophil count < 500 WBC/mm³ (Grade 4)
- Hemolytic anemia Grade 2 (evidence of > 2 g decrease in hemoglobin but does not require blood transfusion) or above.
- Thrombocytopenia-Platelet count < 100,000/mm³ (Grade 1)
- AST/ALT > 3 X ULN (grade 3)

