8. STUDY DRUGS

8.1. Ceftaroline Fosamil Intravenous Study Drug

Ceftaroline fosamil for injection, 400 or 600 mg per vial, is supplied as a sterile pale yellowish-white to light yellow crystalline powder in a single-dose, clear glass 20-mL vial. The excipient L-arginine is added as an alkalizing agent to maintain the pH of the constituted solution between 4.8 and 6.5.

Ceftaroline fosamil is approved in the United States for use in adults with ABSSSI or CABP. Ceftaroline fosamil is limited in pediatric subjects to investigational use only. Refer to the current ceftaroline fosamil IB (Ceftaroline fosamil, 2011) for additional information.

Dosing Information: IV ceftaroline fosamil **15 mg/kg** (or 600 mg if > 40 kg) infused over 120 (\pm 10) minutes q8h (\pm 1 hour) for children **2 years of age – 17 years** of age (inclusive).

IV ceftaroline fosamil **10 mg/kg** infused over 120 (\pm 10) minutes q 8h (\pm 1 hour) for children from **1 year of age to < 2 years** (inclusive).

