12.4. Safety Analysis

Adverse event and serious adverse event monitoring, vital signs and laboratory tests (CBC, BUN, Creatinine, Bilirubin, Alkaline Phosphatase, AST and ALT will be obtained within 24 hours prior to enrollment and weekly during ceftaroline treatment and at the completion of ceftaroline treatment). The Alkaline Phosphatase, Bilirubin, AST/ALT results may not be available prior to enrollment of the patient.

We do not anticipate that the AST/ALT concentrations will be > 3 UNL but if they were to be this elevated, the patient subject will be dropped from the study immediately.

Safety parameters include AEs, SAEs, deaths, clinical laboratory parameters (eg, hematology parameters, chemistry parameters), and vital signs. For each safety parameter, the last assessment made before the first dose of IV study drug will be used as the baseline for all analyses.

The incidences of TEAEs, SAEs, deaths, and discontinuations due to AEs will be summarized by system organ class and preferred term according to the Medical Dictionary for Regulatory Activities by relationship to the study drug, and by severity.

Descriptive statistics of observed results and the change from baseline will be presented for clinical laboratory results, and vital signs. The incidence of PCS laboratory results will be summarized.

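### For same-day repeats of standard-of-care safety tests, Section 9.8.2 keeps only the result nearest to dosing, which can leave an abnormal value out of the PCS counts

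*Combined protocol and SAP*

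**What the plan says.** Section 9.8.2 (Standard of Care Labs) gives the list and the condition: "Record the following local safety labs if performed per standard of care: hemoglobin, hematocrit, WBC, platelet count, BUN, serum creatinine, CRP and ESR". The next sentence is the rule at issue: "If multiple laboratory tests are obtained on the same day, record test results closest to administration of study drug". No section asks for all same-day results, or for the most abnormal one.

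These data feed the primary outcome. Section 6.1 includes "Vital signs and laboratory parameters" among the primary safety assessments. Section 12.4 plans descriptive statistics for observed values and change from baseline, and adds: "The incidence of PCS laboratory results will be summarized". Section 6.4 puts PCS laboratory results in the minimum package for the Data Review Committee (DRC). For baseline, 12.4 specifies that "the last assessment made before the first dose of IV study drug will be used as the baseline for all analyses".

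Section 8.1 sets the dosing pattern: nominally a 2-hour infusion every 8 hours, so three a day.

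**The concern.** A PCS table exists to count extreme values without depending on anyone's judgment of their importance. A rule that keeps one result by its distance from a dose, whatever its value, works against that purpose. Six of the eight tests listed in 9.8.2 are safety tests: hemoglobin, hematocrit, WBC, platelets, BUN and creatinine. The other two, CRP and ESR, are disease markers, which 12.1 uses for time to normalization.

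Standard-of-care draws are also an important source of on-treatment data. Section 9.3 collects CBC, BUN and creatinine on Days 2-14 only when clinically indicated, although 12.4 speaks of weekly tests. What is at stake is a PCS count that is too low, both in the final report and in what the DRC sees while enrollment continues.

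**Working it through.** **1. Denominator.** Section 6.2 gives 18 subjects from an A'Hern design with 0.50 against 0.80, 80% power and a type 1 error of 0.05. This reproduces one-sided: with success at 13 or more of 18, P(X ≥ 13 | 0.50) = 0.0481 and P(X ≥ 13 | 0.80) = 0.867, and no smaller n meets both limits. The point does not depend on this calculation; 18 serves only as the number of treated children.

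**2. Does the rule pick out a sample?** At nominal times, infusion starts are 8 h apart.
- Largest distance to the nearest start: 8/2 = 4 h.
- Gap between the end of one infusion and the next start: 8 − 2 = 6 h. Largest distance to the nearest start or end: 6/2 = 3 h.

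Take two samples, 3 h and 7 h after an infusion start (illustrative times).
- Measured to the nearest start, the distances are 3 h and 8 − 7 = 1 h, so the later sample is kept.
- Measured to the nearest end (at 2 h and 10 h), they are 3 − 2 = 1 h and 10 − 7 = 3 h, so the earlier sample is kept.
- Measured to whichever is nearer, start or end, both are 1 h and the rule gives no answer.

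The selection therefore turns on a definition that the protocol does not supply.

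**3. Direction.** Read PCS incidence as the number of children with at least one PCS value, with baseline fixed as in 12.4. A child who is positive on a subset of results is also positive on the full set. So the count from recorded values cannot exceed the count from all values obtained. This holds whatever the PCS limits are and however often tests are repeated.

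**4. Size of one lost event (Clopper-Pearson).**
- 1/18 = 5.6%. Lower limit 1 − 0.975^(1/18) = 0.1%. The upper limit solves (1−p)^18 + 18p(1−p)^17 = 0.025, giving 27.3%.
- 0/18 = 0%. Upper limit 1 − 0.025^(1/18) = 18.5%.

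**5. How often could this happen?** The documents give no repeat frequency, so this step rests on assumptions. If each of k same-day results is equally likely to be the one kept, a single abnormal result is missed with probability 1 − 1/k: 0.50 for k = 2 and 0.67 for k = 3. Let q be the chance that a child's only PCS value is one of k same-day results, with no other recorded sample showing it. Then the expected number of children lost is 18q(1 − 1/k), and P(at least one lost) = 1 − [1 − q(1 − 1/k)]^18.

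| q (assumed) | k = 2: expected, P(≥1) | k = 3: expected, P(≥1) |
|---|---|---|
| 0.02 | 0.18, 16.5% | 0.24, 21.5% |
| 0.05 | 0.45, 36.6% | 0.60, 45.7% |
| 0.10 | 0.90, 60.3% | 1.20, 71.1% |

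The values of q were chosen to show the arithmetic and are not a forecast.

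**6. Comparison within the protocol.** For temperature, 9.1 and 9.4 record the highest value of the day, and 9.2 and 9.3 the highest after dosing. Keeping the extreme is already the practice for another safety measurement.

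**7. The list itself.** Section 9.8.2 names "hemoglobin, hematocrit, WBC, platelet count, BUN, serum creatinine, CRP and ESR". Table 1.1 and Sections 9.1, 9.3 and 9.4 ask for a CBC with differential, and 7.7.1 has a criterion that needs one: "Absolute neutrophil count < 500 WBC/mm³ (Grade 4". The sections disagree on what is recorded, but this is a separate matter from same-day repeats.

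**The case against.** The strongest reply is that little can be lost.

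- **Scope.** The rule sits in 9.8.2. AST, ALT, bilirubin, alkaline phosphatase and the direct Coombs test are in 9.8.1, which has no such rule. A reader might infer that every laboratory test is affected; the documents do not support that. This stands.
- **Off-study events.** A reader might infer that children crossing a limit in 7.7.1 could be missed. Nothing in 7.7.1, 8.5 or 10.9 ties those decisions to the value chosen for the case report form. This stands.
- **Adverse events.** Section 10.1 counts clinically relevant laboratory abnormalities as examples of adverse events, so such a value should still reach the primary outcome. This stands, with a limit: it depends on the investigator's judgment of relevance, which a PCS count is meant to avoid.
- **Baseline.** A reader might fear that a post-dose Day 1 sample would displace the baseline. Section 12.4 fixes baseline explicitly, 9.1 collects these tests before the first dose, and neither Table 1.1 nor 9.2 schedules CBC or chemistries on Day 1. The documents do not support that fear.
- **Mean change.** If selection is effectively random, mean change from baseline is not biased; only a count of any abnormal value falls.
- **Differential.** It is collected under other sections, so its absence from the 9.8.2 list does not make a same-day value disappear.
- **Frequency.** Nothing in the documents shows how often tests are repeated within a day, or that repeats follow abnormal results. Worst-value counting also has a bias of its own, since it keeps a spurious first value that a repeat corrects.

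None of this removes the core: the rule is written, it is ambiguous under dosing every 8 hours, and the PCS count is the analysis that it can lower.

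**Conclusion.** The point holds in a narrow form. For six standard-of-care safety tests, 9.8.2 reduces same-day repeats to one result by a criterion that is close to arbitrary under this dosing schedule. Relative to all results obtained, the PCS incidence in 12.4 and the PCS results given to the DRC can be understated and not overstated. That direction assumes that incidence counts children and that baseline stays as 12.4 defines it.

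The effect is probably small. One lost event would matter to the reported rate with 18 children, but how likely that is cannot be derived from the documents. A reader might infer that half of all abnormal results vanish. The one-half applies only to a same-day pair with one abnormal member and assumes that either is equally likely to be kept; any other recorded sample showing the abnormality restores the child to the count. This is an inexpensive improvement to data capture. It does not call the sample size or the trial's safety conduct into question.

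**What to change.** Replace the last sentence of 9.8.2 with: *Record all same-day results with collection times.*

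Add to 12.4: *Baseline remains the last sample before the first dose. PCS incidence counts each child by the worst post-baseline value.*

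Separately, reconcile the 9.8.2 list, which has WBC only, with the CBC with differential in Table 1.1 and Sections 9.1, 9.3 and 9.4.

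The cost is a few extra eCRF entries per child and a short addition to 12.4. PCS counts may rise slightly, including from spurious values later corrected by a repeat; with collection times recorded, such pairs can be identified in a listing. Sample size and treatment are unchanged.

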9.8.3. PK Assessments

The pharmacokinetic (PK) outcome measures will include concentrations of ceftaroline, ceftaroline fosamil (prodrug), and ceftaroline M-1 (inactive metabolite) in plasma in subjects on days 2 to 5 of treatment (only one PK sample collected on days 2-5) 4 hours (+/- 30 minutes) after the end of the infusion (before the start of the next infusion). Efforts will be made to obtain 1 PK blood sample (approximately 0.6 mL) at steady state from all subjects who receive ceftaroline fosamil. PK samples may be collected after any infusion of ceftaroline fosamil on those days and before oral switch.

If purulent material is being obtained from bone or sub periosteal abscesses at surgery or via drainage by interventional radiology, we will attempt to obtain specimens for measurement of ceftaroline concentrations.

All samples will be sent to Keystone Bioanalytical, Inc. for analysis.

9.9. Diagnostic Imaging and Non-Pharmacological Assessments

All diagnostic imaging procedures including x-ray or MRIs, in accordance with routine standard of care, will be recorded on the study eCRF. Non-pharmacologic treatments/procedures (such as surgeries) performed in accordance with routine standard of care will be recorded on the study eCRF.

10. SAFETY ASSESSMENTS

Subjects must be seen by a physician or an appropriately trained healthcare professional at every study visit, and the evaluation must be documented. The procedures discussed below will be completed at the designated visits as outlined in Section 10.0.

10.1. Adverse Events

An AE is any untoward medical occurrence in a clinical investigation subject administered a pharmaceutical product and which does not necessarily have to have a causal relationship with this treatment. An AE can therefore be any unfavorable and unintended sign (including an abnormal laboratory finding, for example), symptom, or disease temporally associated with the use of a medicinal product, whether or not considered related to the medicinal product.

Examples of AEs are as follows:

- Changes in the general condition of the subject.
- Subjective symptoms offered by or elicited from the subject.
- Objective signs observed by the Investigator or other study personnel.
- All diseases that occur after the start of the study, including any change in severity or frequency of preexisting disease.
- All clinically relevant abnormalities in laboratory values or clinically relevant physical findings that occur during the study.

10.2. Causality and Severity Assessments

The causality assessment must be recorded on the appropriate AE CRF. Causal relationship must be assessed by answering the following question:

Is there a reasonable possibility the study drug caused the event?

Yes: There is evidence to suggest a causal relationship between the study drug and AE, ie.:

- There is a reasonable temporal relationship between the study drug and the event, and
- The event is unlikely to be attributed to underlying/concurrent disease, other drugs, or other factors, and/or
- Positive de-challenge and/or re-challenge exist

No: There is no evidence to suggest a causal relationship between the study drug and AE, ie.:

- There is no reasonable temporal relationship between the study drug and the event, or
- The subject did not take the study drug, or

- The event is likely to be attributed to underlying/concurrent disease, other drugs, or other factors, or
- The event is commonly occurring in the (study) population independent of drug exposure

The Investigator must provide an assessment of the severity of each AE by recording a severity rating on the appropriate AE screen(s) of the subject's eCRF. *Severity*, which is a description of the intensity of manifestation of the AE, is distinct from *seriousness*, which implies a subject outcome or AE-required treatment measure associated with a threat to life or functionality (Section 11.1.2). Severity will be assessed according to the following scale.

Mild:	Minor awareness of signs or symptoms that are easily tolerated without specific medical intervention.
Moderate:	Discomfort that interferes with usual activities and may require minimal intervention.
Severe:	Significant signs or symptoms that are incapacitating with an inability to work or perform routine activities and/or that require medical intervention.

